## 12.2. Intensity

The relationship to the study drug and the intensity of an AE should be assessed by the Investigator using the following guidelines:

- MILD = Causing no limitation of usual activities; the patient may experience slight discomfort.
- MODERATE = Causing some limitation of usual activities; the patient may experience annoying discomfort; may warrant intervention.
- SEVERE = Causing inability to carry out usual activities; the patient may experience intolerable discomfort or pain; warrants intervention.

## 12.3. Criteria for Determining Relationship to Drug

The Investigator should assess the relationship of the adverse event to the study drug according to the following guidelines:

- DEFINITE = An event that follows a reasonable temporal sequence from administration of the drug or in which the drug level has been established in body fluids or tissue; that follows a known or expected response pattern to the suspected drug; and that is confirmed by improvement on stopping or reducing the dosage of the drug, and reappearance of the reaction on repeated exposure.

- PROBABLE = An event that follows a reasonable temporal sequence from administration of the drug; that follows a known or expected response pattern to the suspected drug; that is confirmed by stopping or reducing the dosage of the drug; and that could not be reasonably explained by the known characteristics of the patient's clinical state.
- POSSIBLE = An event that follows a reasonable temporal sequence from administration of the drug; that follows a known or expected response pattern to the suspected drug; but that could readily be produced by a number of other factors.
- NOT RELATED = Any event that does not meet the above criteria.

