### 4.5.2 Adverse Events

Adverse events (AEs) are monitored from the start of this extension study (informed consent provided by patient at the Baseline visit) until 30 days after administration of the last dose of study drug (end of study drug taper-off).

The AEs will be coded using the most recent Medical Dictionary for Regulatory Activities (MedDRA), Version 9.1. The number and percentage of patients experiencing at least one adverse event will be summarized overall and by body system and preferred term. In any given body system or preferred term patients will only be counted once. Adverse events will further be categorized and summarized by severity and study drug relationship. If the same event for a patient has two different severities, the worst will be taken.

Abnormal laboratory values do not themselves represent adverse events unless they:

- are indicative of a disease or defect, e.g. reduced hematocrit resulting in anemia;

- necessitate intervention, e.g., administration of packed red blood cells or other therapies; and
- result in dose reduction or permanent discontinuation of the drug product.

Worsening of seizure frequency will not be considered an AE but will be captured in the efficacy analysis. Those patients who discontinue their treatment prematurely either during the double-blind period or choose not to enter the open-label extension study should be tapered off their study treatment gradually and will be closely monitored by scheduled clinic visits for worsening of their seizure frequency during this period.

Adverse events will be graded for intensity. An intensity category of mild, moderate, or severe, is defined as

Mild	Causing no limitation of usual activities; the patient may experience slight discomfort
Moderate	Causing some limitation of usual activities; the patient may experience annoying discomfort
Severe	Causing inability to carry out usual activities; the patient may experience intolerable discomfort or pain.

Adverse events will also be graded, by the investigator, for relationship of the AE to study drug. A relationship to study drug category of not related, possible, probable, definite, is defined as

Not Related	No temporal association and other etiologies are likely the cause
Possible	Temporal association, but other etiologies are likely the cause. However, involvement of the study drug cannot be excluded.

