TABLE 17 NUMBER (%) OF PATIENTS REPORTING TREATMENT-EMERGENT ADVERSE EVENTS AT LEAST POSSIBLY RELATED TO STUDY DRUG

TABLE 18 NUMBER (%) OF PATIENTS REPORTING TREATMENT-EMERGENT ADVERSE EVENTS THAT LEAD TO DOSE MODIFICATION/INTERRUPTION

TABLE 19 NUMBER (%) OF PATIENTS REPORTING FATAL TREATMENT-EMERGENT ADVERSE EVENTS

TABLE 20 NUMBER (%) OF PATIENTS REPORTING SERIOUS TREATMENT-EMERGENT ADVERSE EVENTS

TABLE 21 NUMBER (%) OF PATIENTS REPORTING ADVERSE EVENTS THAT CAUSED WITHDRAWAL FROM STUDY

TABLE 22 OBSERVED MEANS AND STANDARD DEVIATIONS OF LABORATORY TEST RESULTS AND CHANGE FROM BASELINE BY MONTH - SERUM CHEMISTRY

TABLE 24 OBSERVED MEANS AND STANDARD DEVIATIONS OF LABORATORY TEST RESULTS AND CHANGE FROM BASELINE BY MONTH – HEMATOLOGY

TABLE 25 OBSERVED MEANS AND STANDARD DEVIATIONS OF LABORATORY TEST RESULTS AND CHANGE FROM BASELINE BY MONTH – URINALYSIS

TABLE 23 NUMBER (%) OF PATIENTS WITH CLINICALLY SIGNIFICANT LIVER FUNCTION TEST RESULTS

TABLE 26 FREQUENCY DISTRIBUTION OF CATEGORICAL LABORATORY TEST RESULTS - URINALYSIS

TABLE 27 SUMMARY STATISTICS OF ELECTROCARDIOGRAM MEASURES

TABLE 28 NUMBER (%) OF PATIENTS EXAMINING QTC INTERVAL BY CATEGORY

TABLE 29 NUMBER (%) OF PATIENTS EXAMINING QTC INTERVAL CHANGE FROM BASELINE BY CATEGORY

TABLE 30 OBSERVED MEANS AND STANDARD DEVIATIONS OF QTC INTERVALS AND CHANGE FROM BASELINE BY MONTH

TABLE 31 OBSERVED MEANS AND STANDARD DEVIATIONS OF VITAL SIGN RESULTS AND CHANGE FROM BASELINE BY MONTH

TABLE 33 NUMBER (%) OF PATIENTS WITH ABNORMAL RESULTS OF PHYSICAL EXAMINATIONS

TABLE 34 NUMBER (%) OF PATIENTS WITH ABNORMAL RESULTS OF NEUROLOGICAL EXAMINATIONS

TABLE 35 NUMBER (%) OF PATIENTS WITH ABNORMAL AUA SYMPTOM INDEX

TABLE 36 DESCRIPTIVE STATISTICS OF RAW OVERALL AUA SCORES  
TABLE 37 NUMBER (%) OF PATIENTS WHO HAD MILD, MODERATE, SEVERE  
AUA SCORES  
TABLE 38 AUA CATEGORY SHIFT FROM BASELINE  
TABLE 39 NUMBER (%) OF PATIENTS WITH ABNORMAL PVR BLADDER  
ULTRASOUND  
TABLE 40 DESCRIPTIVE STATISTICS OF PVR BLADDER ULTRASOUND  
TABLE 41 NUMBER (%) OF PATIENTS WITH A CLINICALLY SIGNIFICANT  
PVR BLADDER ULTRASOUND  
TABLE 42 NUMBER (%) OF PATIENTS TAKING CONCOMITANT  
MEDICATIONS  
TABLE 43 OBSERVED MEANS AND STANDARD DEVIATIONS OF QOL IN  
EPILEPSY (QOLIE-31-P) AND CHANGE FROM BASELINE BY MONTH

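### Protocol 12.3 and SAP 4.5.2 define the same four causality labels differently, and under the protocol's wording a reaction that is neither known nor expected is rated NOT RELATED and left out of Table 17 and Listing 13

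*Protocol*

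**What the plan says.** Protocol 12.3 gives four categories. The three related ones share a response-pattern clause:

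- DEFINITE: suitable timing or a measured drug level, in an event "that follows a known or expected response pattern to the suspected drug; and that is confirmed by improvement on stopping or reducing the dosage", with recurrence on re-exposure.
- PROBABLE: suitable timing, in an event "that follows a known or expected response pattern to the suspected drug; that is confirmed by stopping or reducing the dosage of the drug", and not reasonably explained by the patient's clinical state.
- POSSIBLE: suitable timing, in an event "that follows a known or expected response pattern to the suspected drug; but that could readily be produced by a number of other factors".

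The fourth category is the residual. Under the label NOT RELATED it takes "Any event that does not meet the above criteria".

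Protocol 11.2 says that the four causality categories recorded in the CRF are those the protocol defines. It cites Section 11.3, which in Amendment 2 is the sample-size section; the criteria stand in 12.3.

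SAP 4.5.2 prints the same four labels with other meanings. Possible is "Temporal association, but other etiologies are likely the cause. However, involvement of the study drug cannot be excluded". Not Related is "No temporal association and other etiologies are likely the cause". Neither Probable nor Definite mentions a response pattern. The same section says that the investigator grades the relationship and that the assessment is recorded on the AE page of the CRF. SAP 7 lists Table 17, patients with "TREATMENT-EMERGENT ADVERSE EVENTS AT LEAST POSSIBLY RELATED TO STUDY DRUG"; Listing 13 in SAP 9 is the by-patient counterpart. SAP 4.8 reports no change to the planned analysis.

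**The concern.** The primary objective is long-term safety and tolerability, and Protocol 11.2 promises treatment-emergent events summarised by relationship to study drug. Part of the value of a multi-year extension is finding reactions that are not yet in the drug's profile. A scale that admits only known or expected patterns keeps exactly those reactions out of the related-event counts, whatever the timing, dechallenge or rechallenge evidence.

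The two documents also attach different meanings to the same recorded word, so a reader of Table 17 cannot tell what 'related' means in it. Amendment lag does not explain this. The SAP says it was written to Amendment 1, and section 12.3 of that amendment carries the same clause, as does section 11.3 of the 2006 protocol.

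**Working it through.** The plan gives no figure to reproduce. The check is whether the wording does what it appears to do.

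1. Code Protocol 12.3. Let T = suitable timing, L = drug level established, P = known or expected pattern, D = improvement on stopping or reducing the dose, R = recurrence on re-exposure, A = another explanation readily available. Apply in this order:
   - DEFINITE if (T or L) and P and D and R
   - PROBABLE if T and P and D and not A
   - POSSIBLE if T and P and A
   - NOT RELATED otherwise

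   The 'or' in DEFINITE joins only T and L. It does not waive P.

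2. P absent. The other five inputs give 2^5 = 32 combinations, and all 32 are NOT RELATED, including T = D = R = 1 with A = 0. This counts inputs to the rule, not patients. It confirms that the clause is necessary and says nothing about how often an event fails it.

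3. P present.
   - DEFINITE: D = R = 1, three of the four (T, L) pairs, A free: 3 × 2 = 6
   - PROBABLE: T = 1, D = 1, A = 0, R = 0, L free: 2
   - POSSIBLE: T = 1, A = 1, D and R not both 1, L free: 3 × 2 = 6
   - NOT RELATED: 32 − 6 − 2 − 6 = 18

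   With T = 0 there are 16 combinations, of which 2 are DEFINITE (L = D = R = 1, A free), so 14 of the 18 lack timing. The other 18 − 14 = 4 have T = 1, D = 0, A = 0 (L and R free). This is a second gap: a well-timed event with an expected pattern, no dechallenge information and no other explanation meets neither PROBABLE nor POSSIBLE and also falls to NOT RELATED.

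4. Put the same temporally linked event on both scales.

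| Event | Protocol 12.3 | SAP 4.5.2 |
|---|---|---|
| Neither known nor expected; dechallenge and rechallenge positive; no other cause | NOT RELATED | Definite |
| Neither known nor expected; other causes likely; drug not excluded | NOT RELATED | Possible |
| Expected; no dechallenge information; no other cause | NOT RELATED | at least Possible |

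5. Ask whether the SAP repairs the rating. Its only rule that assigns causality covers a missing rating, which takes the worst case. A recorded NOT RELATED stands, so all three rows are absent from Table 17 and Listing 13 if sites rated by the protocol.

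6. Ask what is untouched. Tables 15, 18, 19, 20 and 21 (all treatment-emergent events, dose modification, fatal, serious, withdrawal) and Listings 11 and 12 do not depend on causality. Protocol 12.4 has serious events reported whatever their relatedness or expectedness.

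**The case against.** Several limits are fair, and they stand.

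- A reader might infer that a site is bound to tick NOT RELATED. Protocol 12.3 calls the definitions guidelines that the investigator should use, which leaves room for judgement.
- 'Expected' is not defined. It could cover effects anticipated from pharmacology or animal findings, such as the bladder effects in Protocol 7.3, without earlier human cases. The affected class is narrower than every event not seen before with the drug.
- The wording in front of sites is not shown. Protocol 11.2 points to the protocol's definitions; SAP 4.5.2 prints its own and says the assessment is on the CRF page. If the CRF carries the SAP wording, the omission from Table 17 does not follow. The conflict would still need settling.
- A reader might infer that the study can only confirm known reactions. The unfiltered tables say otherwise. Listings 11 and 12 show relationship, action taken and outcome for each event, so dechallenge can be read for events rated NOT RELATED. Protocol 10.3.4 and 10.20.1 also require expedited reporting of low neutrophil counts, serious haematological events or infections, and withdrawals for such reasons.
- A reader might infer that the outputs would describe these events as lacking a temporal association. The shells for Table 17 and Listing 13 print no causality definitions.

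What does not stand is that these limits make the scale harmless. A related-event table filled under one definition and explained under another cannot be interpreted, and the unfiltered tables do not correct the related-event rates or the rating of non-serious events.

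**Conclusion.** The point holds in a confined form and should be fixed. It does not reach must-fix, because the main safety tables and serious-event reporting are unaffected.

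The conflict between the two sets of definitions is plain on the page. The omission from Table 17 and Listing 13 rests on two conditions: sites follow Protocol 12.3 as written, and the event is neither known nor expected, or it falls in the second gap. Under those conditions the related-event percentages are too low by the SAP's own definition. By how much cannot be derived from the documents. A count of zero in Table 17 for every new kind of event is a tempting conclusion, but it assumes the CRF wording and treats guidelines as a fixed algorithm; the documents establish neither.

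**What to change.** 1. State which causality definitions the CRF carries.
2. Put one set of definitions in Protocol 12.3 and SAP 4.5.2. The SAP's existing scale would serve.
3. Remove the response-pattern clause as a necessary condition from all three related categories, DEFINITE included.
4. Make NOT RELATED a positive judgement instead of the residual, and check that every temporally linked event has a category, including one with no dechallenge information and no other cause.
5. Correct the cross-reference in Protocol 11.2 from Section 11.3 to 12.3.
6. For events already rated under the protocol's present wording, keep the recorded rating. State in the SAP and in a footnote to Table 17 which scale produced it. Add a listing of all NOT RELATED treatment-emergent events with onset after first dose, showing action taken and outcome. Do not limit it to events that improved on a dose change: Possible does not need dechallenge, and a selection made open-label with outcomes known would miss events where dosing continued unchanged.

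The cost is a wording amendment, a site memo and one extra listing. The related-event percentage may rise slightly.

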#### 12.4. Reporting of Adverse Events

All AEs should be recorded on the appropriate CRFs. All SAEs, whether or not deemed drug-related or expected, must be recorded on the CRFs and SAE forms and reported by the Investigator to the CRO (Quintiles Pharmacovigilance) assigned by the Sponsor within 24 hours by telephone and facsimile.

Complete details of SAE contact information for Quintiles Pharmacovigilance will be provided to sites in each of the participating countries in the Study Reference Manual.

A written report for an SAE must follow within 24 hours of the initial notification, including a full description of the event and any sequelae. This includes events that occur while enrolled in the study or within the Follow-Up Period. The Investigator shall comply with all applicable regulations and report all SAEs according to the requirements of their Institutional Review Board (IRB), Independent Ethics Committee (IEC) or Research Ethics Board (REB).

##### 12.4.1. Adverse Events Follow-Up

AEs will be recorded from the start of this extension study (informed consent provided by patient at the Baseline visit) until 30 days after administration of the last dose of study medication (end of study medication taper-off). All post-treatment events will be collected through spontaneous reporting by the patient. All AEs and SAEs will be followed until the event resolves, the condition stabilizes, the event is otherwise explained, or the patient is lost to follow up. The Investigator is responsible for ensuring that follow up includes any supplemental investigations as may be indicated to elucidate the nature and/or causality of the AE. This may include additional laboratory tests or investigations, histopathological examinations, or consultation with other health care professionals, as is practical.

### **13. DOSE MODIFICATIONS**

Patients will be treated with 600-1200 mg/day of retigabine as an adjunct therapy to their current antiepileptic medications (AEDs) or vagal nerve stimulation as established in Study VRX-RET-E22-302.

If, in the opinion of the Investigator, the patient was not receiving the maximum effective dose, the dose could be increased in weekly intervals of 150 mg/day, up to a maximum of 1200 mg daily (i.e., 400 mg TID). If adverse events considered to be secondary to retigabine occur, the total daily dose could be reduced by 150 mg/day every week, at Investigator discretion, as long as the dose is within 600-1200 mg/day.

After the patient has entered open-label treatment, the Investigator may add new AEDs, as long as these are approved AEDs. In addition, the existing background AED therapy can be adjusted to achieve the best efficacy/safety ratio, as needed, per Investigator discretion. If necessary, in the Investigator's judgment, all background AEDs can be discontinued to achieve monotherapy with retigabine.

Patients who permanently discontinue open-label treatment will have their dose tapered by one-third every week.

If a patient experiences a serious adverse event that is categorized to be "life-threatening," all study medication must be discontinued immediately.

All dose modifications and reason(s) must be documented in the patient's source documents and the CRF.

### **14. MONITORING**

The Sponsor or designee will monitor this clinical trial through visits scheduled to check the adequacy of staff and facilities, and to ensure adherence to the protocol, study procedures and applicable regulations. The clinical monitor will also assess proper CRF completion and retention. The Investigator and clinical staff are expected to allocate sufficient time to permit adequate review of the study's progress. The Investigator will permit trial-related monitoring, audits, IRB/IEC review and regulatory inspection(s), providing direct access to source data/documents.

### **15. QUALITY ASSURANCE AND QUALITY CONTROL**

The Sponsor or designee will implement and maintain quality assurance and quality control systems with Standard Operating Procedures (SOPs) to ensure that this clinical trial is conducted and data are generated, documented (recorded) and reported in

compliance to the protocol, Good Clinical Practice (GCP) standards, ICH and other applicable regulations.

The Sponsor is responsible for securing agreement among collaborating parties to ensure direct access to clinical-trial-related sites and material to ensure that all data are reliable and have been processed correctly.

## **16. DRUG ACCOUNTABILITY**

The Investigator must maintain accurate records of the study medication received from the Sponsor, including date received, number of units received and lot number. The Investigator must also ensure that the drug supplies are kept secured and accounted for with access limited to those authorized by the Investigator. The study coordinator or designee must maintain accurate records of all study medication received to be able to reconcile the dispensing logs at the end of the study. The study drug records must be readily available for inspection by the study monitor and/or auditor. No medication (new or used) can be returned to the Sponsor (or its designee) or disposed of at the research unit until the Sponsor's clinical monitor has verified the accuracy of the study medication records at the site and indicated whether the medication should be destroyed at the site or returned to the Sponsor (or its designee), in which case the study monitor must indicate the name and address of the individual to whom the returned materials should be shipped.

## **17. LABELING AND PACKAGING OF STUDY MEDICATION**

The study drug will be packaged and labeled in a manner consistent with the study design and applicable regulations. The study drug shall be identified as an investigational compound. The study protocol number will be identified on the unit label. Designated site personnel shall record the drug unit on the drug dispensing logs when the study drug is dispensed.

Each bottle of retigabine tablets (50 mg, 100 mg, or 300 mg per tablet) will be labeled with the protocol number, a unique package number, the name of the study medication, the use-by date, the Valeant address, and any additional information required by local regulations. In addition, spaces will be included for recording patient number/initials, visit number, and dated dispensed. Specific dosage instructions will be provide separately to the patient. A sufficient supply of study medication will be provided to each site for completion of trial, based on the number of patients enrolled, study visit schedule, and the daily doses of patients.

All study medication will be dispensed by the pharmacy or an appropriately qualified member of the study staff assigned by the Principal Investigator to this task.

## 18. DATA HANDLING AND RECORDKEEPING

### 18.1. Records

The Investigator must maintain all documents and records, copies or originals, relating to the conduct of this trial. This documentation includes, but is not limited to protocols, CRFs, advertising for patient participation, AE reports, patient source data, correspondence with health authorities and IRB/IEC/REB, consent forms, Investigator's curriculum vitae, monitor visit logs, laboratory reference ranges and laboratory certification or quality control procedures and laboratory director curriculum vitae. The Investigator and affiliated institution should maintain the trial documents as required by the applicable regulations. The Investigator and affiliated institution should take measures to prevent accidental or premature destruction of documents. Clinical trial documents must be kept in the clinical site's archives indefinitely, unless written authorization is obtained from the Sponsor.

Federal regulations require that records of drug disposition, CRFs, and all reports of this investigation shall be retained by the Investigator for a minimum of 15 years after notification by Valeant that the regulatory authorities have been notified of the study's termination, or 2 years after approval of the marketing application. If the Investigator is unable to retain the study documents for the required amount of time, Valeant must be informed of the individual who will be assuming this responsibility. These documents shall be retained for a longer period, however, if required by applicable regulatory requirement(s) or if needed by the Sponsor.

### 18.2. Case Report Forms

All entries on a CRF are ultimately the responsibility of the Investigator, who is expected to review each form for completeness, accuracy and legibility before signing. All forms must be filled out by using black ink. Errors should be lined out but not obliterated and the correction inserted, initialed, dated and an explanation provided (if not evident). A CRF must be completed for each participant who has given informed consent. The CRFs and source documents must be made available to the study monitor for review at the time of the monitoring visits.

